**[contact], [contact]**

## **1. Purpose of the Study and Background**

### **1.1 Purpose of the Study:**

The study objective is to determine whether use of netarsudil significantly reduces the rate of steroid-associated intraocular pressure (IOP) elevation when used by cornea transplant recipients long-term as an adjunct to prednisolone acetate (PA) 1% ophthalmic solution (used to prevent transplant rejection).

### **1.2 Background**

Topical corticosteroids are commonly used to control postoperative ocular inflammation. They are also the mainstay for preventing and treating corneal transplant rejection and for treating ocular conditions involving immune hyper-reactivity. The principal drawbacks include steroid-induced ocular hypertension and steroid-induced glaucoma. The incidence varies with the type of glucocorticoid and its formulation, the dosing frequency, and the treatment duration.

Prednisolone acetate 1% ophthalmic solution is the most commonly used topical corticosteroid in the U.S. Treatment duration ranges from a few weeks, for controlling postoperative inflammation, to years, for preventing cornea transplant rejection. Up to 35% of patients without a prior glaucoma diagnosis and up to 80% with pre-existing glaucoma experience clinically significant post-keratoplasty IOP elevation with long-term topical corticosteroid use. Intraocular pressure elevation is associated with reduced visual acuity and increased risk of transplant failure.

Corneal transplantation offers a unique opportunity to evaluate potential methods for preventing IOP elevation associated with long-term use of topical corticosteroids, without the confounding factors present with immune hyper-reactivity disorders.

### **1.3 Study Design**

- Prospective, randomized, double-masked, placebo-controlled clinical trial
- Main Outcome Measure
  - Rate of intraocular pressure elevation

## **2.0 Characteristics of the Research Population**

2.1 **Number of Subjects:** up to 186 cornea transplant (endothelial keratoplasty) patients will be enrolled.

2.2 **Gender of Subjects:** both men and women will be enrolled

2.3 **Age of Subjects:** 18-90 years of age. The rationale for not including minors is that endothelial keratoplasty is performed to treat endothelial dysfunction, a condition usually seen in adults over 40 years of age.

2.4 **Racial and Ethnic Origin:** Subjects may be of any racial or ethnic origin.

2.5 **Inclusion criteria:** the following are requirements for study inclusion:

- At least 18 years of age
- Male or female patient undergoing Descemet membrane endothelial keratoplasty
- Patient is able and willing to administer eye drops.
- Patient is able to comprehend and has signed the Informed Consent form.
- Patient is likely to complete the nine-month course of the study.

**2.6: Exclusion criteria:**

- A patient exhibiting pre-operative intraocular inflammation.
- A patient with a known sensitivity to any of the ingredients in the study medications
- A patient who has a condition (i.e., UNCONTROLLED systemic disease) or is in a situation which in the investigator's opinion may put the patient at significant risk, may confound the study results, or may interfere significantly with the patient's participation in the study
- A patient with abnormal eyelid function.
- A patient that is exhibiting active corneal ulceration, keratitis, or conjunctivitis, or who has a history of herpetic keratitis.
- A patient who has been diagnosed with uncontrolled glaucoma, prior aqueous shunt or trabeculectomy, or with preoperative IOP > 22 mm Hg in the potential study eye.
- Presence of any ocular disease that would interfere with the evaluation of the study treatment. However, patients with a history of cystoid macular edema, age-related macular degeneration, corneal neovascularization, and other non-interfering comorbidities may be enrolled.
- A patient with a history of non-compliance with using prescribed medication.
- A patient who is concurrently involved in or participated in another randomized clinical trial within 30 days prior to enrollment in this study.
- Patients who are pregnant or planning to become pregnant within the duration of the study

**2.7 Vulnerable Subjects:** No potentially vulnerable subjects will be enrolled because there may be no direct benefit to the patient; rather, important knowledge which may benefit future subjects is being sought. As such, the direct benefit would not outweigh risks for vulnerable populations.

Minors will not be enrolled into this study because the conditions being studied under this protocol are not typical problems for minors. Endothelial keratoplasty is performed to treat endothelial dysfunction, a condition usually seen only in older (>40 years of age) adults.)

Pregnant women will not be enrolled into this study as potential risks and harm to the fetus is unknown.

This study plans to exclude any person who does not speak English as non-English speaking patients are not normally seen at the study site so a translator would not be available to translate the consent form into the patient's native language.

### **3.0 Methods & Procedures**

#### **3.1 Study procedures and assessments.**

- **Screening and Enrollment:** Prospective subjects will be considered for entry into the study. Subjects meeting the inclusion and exclusion criteria will be informed of the opportunity to participate in the study. Subjects will be entered into the study after providing written informed consent. Each subject will be instructed that if they decide not to participate, they may withdraw at any time.
- **Randomization:** Netarsudil ophthalmic solution 0.02% and placebo eye drops will be dispensed to study subjects in 2.5 ml bottles, identical in appearance. A designated, unmasked, dosing coordinator will apply a coded sticker to each bottle. A computer generated randomization table will be generated. During the routine follow up exam 1 or 2 days after transplantation, the study subject will be randomly assigned to receive netarsudil or AR-13324 placebo (netarsudil vehicle). Both the subject and the investigator will remain masked as to the assigned treatment. If a study participant elects to have both eyes enrolled in the study, the dosing coordinator will automatically assign the second eye to the opposite treatment group from that of the first eye.
- **Study Treatment Regimen:** Subjects will be instructed to instill the assigned eye drop into the study eye once nightly for the 9-month study duration. As standard of care to prevent cornea transplant rejection, subjects will use prednisolone acetate 1% eye drops 4 times daily for the first 3 months, then 3 times daily during month 4, twice daily during month 5, and once daily during months 6 to 9.
- **Study Drug Accountability:** Subjects will be asked to bring back to the clinic all study bottles, both used and un-used. All study drug bottles will be reconciled and recorded.
- **Rescue Medication:** if a study subject develops IOP elevation (a measurement  $\geq 24$  mm Hg or an increase over the screening pre-operative reading of  $\geq 10$  mm Hg), the dosing coordinator will be notified. If the affected eye was assigned to the placebo group, the subject will be offered the opportunity to crossover to the netarsudil group to determine whether that adequately reduces IOP. Depending upon the severity of the IOP increase, the investigator may decide whether it is in the patient's best interest to reduce corticosteroid strength and/or dosing frequency and/or initiate use of approved glaucoma medications.
- **Examinations:**

- Schedule: Each subject will be examined at screening, 1, 3, 6 and 9 months after endothelial keratoplasty as detailed in Table 1. The examination schedule and procedures are standard of care for endothelial keratoplasty patients.
- Procedures: At 5 day, 1, 3, 6, and 9 month exams, medical and ophthalmic histories will be updated, adverse events will be recorded, and measurements of visual acuity will be made. At 1, 3, 6 and 9 month exams, measurements of manifest refraction, corneal thickness (pachymetry) and intraocular pressure will be made. Corneal endothelial cell density will be measured by specular or confocal microscopy if possible.. A slit lamp examination will be performed to assess the health of the transplant and document any conjunctival or lid hyperemia, stromal inflammation, superficial punctate keratitis, other surface toxicity of the cornea, neovascularization of the cornea, cells or flare in the anterior chamber, or evidence of transplant rejection.
- Records release: Subjects may be asked to sign a records release form in case the subject sees another eye specialist while enrolled in the study. This will allow the investigator to determine if there is a rejection episode or elevated intraocular pressure at examinations made with other physicians. The primary outcome (intraocular pressure) is a routine ophthalmic exam procedure, so the subject may have some exams performed by a local eye doctor if returning to the study site for all exams is too burdensome.
- Unscheduled examinations: Subjects will be instructed to return for extra examinations if they note any problems with the eye or any early signs of a possible rejection episode, such as a change in vision, redness to the eye, increased light sensitivity, burning sensation, or foreign body sensation.
- Study completion: Subjects will be considered to have completed the study after they complete the 9-month examination.
- Subject withdrawal or discontinuation: Each subject may voluntarily discontinue the study at any time they choose. Subjects who cannot complete the study for administrative reasons (e.g., non-compliance, failure to meet visit schedule, etc.) will be discontinued from the study. Discontinued subjects may be replaced. For

subjects withdrawn from the study, the same measurements and assessments should be performed as done at the 9-month exit exam. Adverse events should be followed up until resolution or stabilization of the adverse event.

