**Table 1**

	Screening	Randomization (1 or 2 days after DMEK)	5 day after DMEK	4 ( $\pm$ 2) weeks after DMEK	3 ( $\pm$ 1) months after DMEK	6 ( $\pm$ 1) months after DMEK	9 ( $\pm$ 1) months after DMEK
Informed Consent	X						
Inclusion/Exclusion Criteria	X						
Medical and ophthalmic history	X	X	X	X	X	X	X
Adverse Events		X	X	X	X	X	X
Uncorrected visual acuity (Snellen)	X	X	X	X	X	X	X
Assignment to netarsudil or placebo		X					
Corrected distance visual acuity (Snellen)	X			X	X	X	X
Manifest refraction	X			X	X	X	X
Endothelial cell density (if possible)	X			X	X	X	X
Intraocular pressure	X			X	X	X	X
Ultrasonic pachymetry	X			X	X	X	X

**3.2 Data Analysis and Data Monitoring:** The primary outcome measure is the incidence of clinically significant IOP elevation (defined as IOP  $\geq$  24 mm Hg or a relative increase over the baseline reading of  $\geq$  10 mm Hg). Previous study results conservatively suggest that the rate of IOP elevation will be 20% or greater in the placebo-control arm. Based on the mechanism of action and clinical trial results, we estimate that the relative odds ratio will be 0.25 in the netarsudil study arm. A sample size of 84 per study arm (total = 168) would provide 80% power to detect a statistically significant difference between groups at a 5% significance level (two-sided test). Assuming up to 10% drop out, the required recruitment is 186 study eyes.

Statistical analysis will be conducted on an intent-to-treat basis (i.e. all randomized subjects will be included in the analysis). Data will be analyzed with Statistical Analysis Software (SAS Version 9.4, SAS Institute, Cary, NC) using Kaplan Meier survival analysis and proportional hazards analysis.

**3.3 Data Storage and Confidentiality:** Research data will be stored in a locked cabinet or locked room and on a password protected server to prevent unauthorized access to data. The investigators and research staff will have access to the data. Subject identifiers will be removed and data will be aggregated for publication or presentation of study results.

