#### **4.0 Risk/Benefit Assessment**

##### **4.1 Risks and Anticipated Adverse Events:**

Risks: This study is considered moderate risk. Netarsudil is an investigational drug - a New Drug Application (NDA) was recently submitted to the U. S. Food and Drug Administration.

A number of complaints and complications are anticipated in patients who have received a cornea transplant, regardless of whether they participate in this study. Therefore, the presence or absence of the following anticipated complaints and complications in the study eye will be recorded on the electronic case report form (eCRF) for each exam rather than on separate adverse event forms.

- Complaints of ocular discomfort: (examples include: eye pain, irritation, burning, itching, scratchy feeling, foreign body sensation, tired/fatigued feeling, achy/tender/sore feeling, pressure sensation, tightness, twinge/twitchy feeling, dry eyes, tearing/watering, eye redness)
- Complaints of visual symptoms or disturbances: (examples include: glare or fluctuating vision, haloes around lights, diplopia, blurry, hazy, cloudy, filmy or out of focus vision, ghosting or shadowing, difficulty reading, difficulty with night driving, floaters, spots in vision, light sensitivity, decreased vision, light reflections from intraocular lens or peripheral iridotomy).
- Increased ptosis (within the first 6 months of surgery)
- Puffy eyelids (within the first 3 months of surgery)
- Delayed resolution of corneal haze or edema (within the first 6 months of surgery)
- Subconjunctival hemorrhage (within the first 3 months of surgery)
- Epithelial defect (within the first month of surgery)
- Folds in the transplant

- Partial graft detachment without further intervention
- Development of capsular haze
- Superficial punctate keratitis
- Pupillary block (within the first 3 months of surgery)

Adverse events: The type, severity, duration and frequency of the following anticipated adverse experiences and any other unanticipated ocular adverse events will be tabulated. If a patient experiences an adverse reaction, appropriate medical treatment will be provided. Examples may include:

- Graft detachment which requires intervention
- Immunologic graft rejection episode
- Graft failure and/or regraft
- Intraocular pressure elevation which requires intervention
- Development of capsular haze which requires intervention
- Iris synechia
- Cystoid macular edema
- Iritis

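### No rule attributes safety data after placebo-to-netarsudil crossover; under intent-to-treat, the only rule stated, any excess harm of netarsudil would be understated

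*Combined protocol and SAP*

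**What the plan says.** **Crossover.** Under Rescue Medication in section 3.1, an eye qualifies when its IOP is at least 24 mm Hg or shows "an increase over the screening pre-operative reading of" at least 10 mm Hg. The rule continues: "If the affected eye was assigned to the placebo group, the subject will be offered the opportunity to crossover to the netarsudil group". The stated aim is to see whether IOP then falls enough. No duration is given and no switch from netarsudil to placebo is described. The investigator may also reduce the steroid or start approved glaucoma medication, in either arm.

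**Follow-up.** Section 3.1 defines completion as the 9-month examination. Nothing says that a crossed eye leaves follow-up.

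**Safety data.** The slit-lamp examination documents hyperemia, "superficial punctate keratitis, other surface toxicity of the cornea, neovascularization of the cornea" and other findings. Section 3.1 also states: "Corneal endothelial cell density will be measured by specular or confocal microscopy if possible". Table 1 schedules cell density and corrected acuity at screening, 4 weeks and 3, 6 and 9 months. Section 4.1 has many surface complaints noted as present or absent at each exam instead of on adverse event forms. Of adverse events it says: "The type, severity, duration and frequency of the following anticipated adverse experiences and any other unanticipated ocular adverse events will be tabulated".

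**Analysis.** Section 3.2 states: "Statistical analysis will be conducted on an intent-to-treat basis (i.e. all randomized subjects will be included in the analysis"). The methods named are Kaplan-Meier and proportional hazards. No safety set, as-treated table or rule for post-crossover data appears. Table 1 lists treatment assignment only at randomization and has no crossover entry. Section 4.2 has the DSMC review adverse events every 6 months and does not describe the tables.

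**The concern.** The contamination runs one way. Some placebo eyes may spend part of the 9 months on netarsudil, but no netarsudil eye moves to placebo. Intent-to-treat suits the primary outcome, because the event that opens crossover is the primary event itself. It suits harms poorly. An eye assigned to vehicle that develops punctate keratitis or hyperemia two months after starting netarsudil would be a placebo case in a table by assigned arm. If netarsudil raises the risk of that finding, the placebo rate goes up and the difference between arms goes down.

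This matters because section 4.1 describes netarsudil as investigational and the study as moderate risk, and the data concern the surface and endothelium of a fresh graft. Where a patient has both eyes enrolled, section 3.1 gives the second eye the opposite treatment. If the placebo eye then crosses, both eyes are on netarsudil and the within-patient comparison is lost from that date.

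**Working it through.** **1. The plan's own figure.** Section 3.2 assumes that "the rate of IOP elevation will be 20% or greater in the placebo-control arm", with an odds ratio of 0.25, two-sided 5% and 80% power.
- Netarsudil rate: 0.25 × (0.20/0.80) = 0.0625; 0.0625/1.0625 = 5.88%.
- Two proportions, unpooled variance: 7.849 × (0.20 × 0.80 + 0.0588 × 0.9412)/(0.1412)² = 84.8, so 85 per arm against the stated 84.
- Dropout: 168/0.9 = 186.7 against the stated 186.

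The figures reproduce closely. Only the 20% is used below.

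**2. How many eyes could cross.** With 186/2 = 93 placebo eyes, 93 × 0.20 = 18.6 become eligible (84 × 0.20 = 16.8 if only the evaluable number is counted). Section 1.2 gives a higher figure: "Up to 35% of patients without a prior glaucoma diagnosis" have clinically significant IOP elevation on long-term topical steroid. At 35%, 93 × 0.35 = 32.6 become eligible.

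**3. How much exposure (assumed).** Suppose every eligible eye accepts, first events fall equally at months 1, 3, 6 and 9, and netarsudil continues to month 9.
- Months left: 8, 6, 3 and 0; mean (8 + 6 + 3 + 0)/4 = 4.25.
- Eyes actually exposed: 18.6 × 0.75 = about 14 (15% of 93).
- Share of placebo follow-up: 18.6 × 4.25/(93 × 9) = 79/837 = 9.4%.

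**4. Dilution.** Let q1 and q0 be the 9-month risks of a harm on netarsudil and vehicle (assumed), h = −ln(1 − q) the matching constant hazards, f the fraction of follow-up left after crossing, and c the share of placebo eyes that cross.
- Risk in a crossed eye: qc = 1 − exp[−(f·h1 + (1 − f)·h0)].
- Placebo risk by assigned arm: (1 − c)·q0 + c·(mean qc).

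*30% vs 10%* (h1 = 0.357, h0 = 0.105). For f = 8/9, 6/9, 3/9 and 0, qc = 28.0%, 23.9%, 17.2% and 10.0%; mean 19.8%. Placebo: 0.80 × 10% + 0.20 × 19.8% = 12.0%.

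*50% vs 10%* (h1 = 0.693). qc = 46.6%, 39.2%, 26.0% and 10.0%; mean 30.5%. Placebo: 0.80 × 10% + 0.20 × 30.5% = 14.1%.

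| Assumed risks | Uptake (c) | Placebo, by assigned arm | Risk ratio | Risk difference | Shrinkage |
|---|---|---|---|---|---|
| 30% vs 10% | none | 10.0% | 3.0 | 20.0 points | – |
| | 100% (0.20) | 12.0% | 2.5 | 18.0 points | 10% |
| | 50% (0.10) | 11.0% | 2.7 | 19.0 points | 5% |
| 50% vs 10% | none | 10.0% | 5.0 | 40.0 points | – |
| | 100% (0.20) | 14.1% | 3.5 | 35.9 points | 10% |
| | 50% (0.10) | 12.0% | 4.2 | 38.0 points | 5% |

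**5. Range with timing.** If every crossed eye has the same fraction f left, the 30% vs 10% difference of 20 points becomes:

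| c | f = 0.33 | f = 0.67 | f = 1.0 |
|---|---|---|---|
| 20% | 18.6 points (7% lost) | 17.2 (14%) | 16.0 (20%) |
| 35% | 17.5 points (12% lost) | 15.1 (24%) | 13.0 (35%) |

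At f = 1 the loss equals c, so the share of placebo eyes that cross is the ceiling.

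**The case against.** The strongest answer is that the plan is silent, not wrong. Section 3.2 explains intent-to-treat as a rule about who is included and sets it beside the time-to-event methods for the primary outcome. Section 4.1 defines no columns. A reader might infer that the plan commits itself to charging post-crossover harms to placebo. It does not say so; that result follows only if its single analysis rule is carried over to safety. This stands, and it is why the point concerns a missing attribution rule.

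Other inferences also go further than the text:
- **Size.** It is tempting to treat the 15% of placebo eyes exposed as carrying the full 9-month netarsudil risk. That gives placebo rates of 13% and 16% and risk ratios of 2.3 and 3.1. Those eyes would have only 3 to 8 months on the drug, so 2.5 and 3.5 are the consistent figures.
- **Duration and uptake.** Crossover is offered, its stated aim is to test IOP control, and steroid reduction or glaucoma medication may be used. Use to month 9 and full uptake are assumptions.
- **DSMC.** Section 4.2 gives no table format, so it cannot be said that the committee would see a diluted comparison.
- **Link to a positive result.** The number of crossovers depends on the placebo event rate, not on the treatment effect.

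It is also fair to say that much may be recoverable: the dosing coordinator is notified at the threshold, bottles are reconciled, and complaints are recorded exam by exam. But no section ties these records to the safety analysis.

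Finally, replacing the by-arm table with one by drug received would bring its own bias. Placebo follow-up would be cut only for eyes with raised IOP, which section 1.2 links to poorer acuity and graft failure, while netarsudil eyes with the same event stayed in. That stands and shapes the fix.

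**Conclusion.** The point holds as a gap in the safety analysis. The plan allows one-way crossover, keeps following the eyes, and states no rule for attributing what is then observed. Under the one rule it does state, any excess harm of netarsudil is understated: by about 10% in the scenario worked above, about 5% at half uptake, and never by more than the share of placebo eyes that cross (20%, or 35% at the higher event rate). All of this assumes that netarsudil does raise the risk in question. Harm rates, uptake, timing and duration are not in the documents.

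A reader might infer that crossover also biases the primary result. It does not: the trigger uses the same thresholds as the primary event, and the only pre-treatment IOP in Table 1 is the screening reading, so a placebo eye has had its first event before it can switch. The exposure is confined to adverse events, slit-lamp findings and later cell density and acuity. It should be corrected, but it does not threaten the main conclusion.

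**What to change.** In section 3.2 and the eCRF, leaving the crossover rule itself as it is:

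1. Record the date of the first netarsudil dose after crossover, and the stop date if it is stopped.
2. Keep intent-to-treat for the primary outcome, and keep a safety table by assigned arm.
3. Add a table of adverse events and slit-lamp findings by drug in use at onset, with three columns (netarsudil as assigned, placebo before crossover, netarsudil after crossover) and rates per exposure time.
4. For month 6 and 9 endothelial cell density and visual acuity, keep the comparison by assigned arm and add a descriptive display that identifies crossed eyes.
5. Supply both safety tables to the DSMC.

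**Cost.** A paragraph of analysis text and the date fields. The added table is not a randomised comparison, and its placebo column loses follow-up only from eyes with raised IOP. It must therefore be read beside the by-assigned-arm table and cannot replace it. Steroid changes or glaucoma medication after an event still complicate post-event data in both arms; neither table removes that.
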